8.1.2. Key Secondary, Supplemental, and Sensitivity Analyses of Time to Recovery

For all supplemental and sensitivity analyses of the primary outcome, p-values may or may not be reported, and 95% confidence levels will be used for confidence interval estimates.

The primary analysis will be repeated in the As Treated analysis population where subjects who are not treated will be censored at randomization. The tabular and graphical summaries described in the previous section will be replicated for this As Treated analysis. For the key secondary outcome measure, the analysis will follow as described in Section [8.1.1](#), excluding subjects with a baseline ordinal score of 6. The primary analysis will also be repeated using the Modified Oxygen Use ordinal scale described in Section [4.3](#) ([Table 11](#)).

Sensitivity analyses will be performed using Cox proportional hazards models to estimate the hazard ratio ([Table 12](#)). First, an mITT analysis will be performed in which subjects who die prior to recovering are treated as experiencing a competing risk in the Fine-Gray proportional hazards regression model. Second, a Cox model will be fit with binary indicators for treatment group and baseline ordinal score (4, 5, or 6 and separately 4+5 vs. 6) as well as a treatment * baseline ordinal score (as a continuous variable) interaction terms. The models will be fit to the mITT analysis population. The treatment group hazard ratios and CIs will be reported for both sets of models and the interaction term p-value will be reported for the interaction models. The tabular summary will also include results from an analysis of time to recovery controlling for age and duration of symptoms as continuous covariates and baseline d-dimer and CRP values as continuous covariates.

The primary analysis will also be repeated using the other subgroups defined in Section [6.4](#) in place of disease severity. Each subgroup will be considered separately and the tabular and graphical summaries described in the previous section will be replicated for each subgroup. A forest plot will be generated to display the overall treatment hazard ratio estimate and CI from each of the within-subgroup analyses ([Table 13](#)).

As noted in Section [6.4](#), analyses that take into account concomitant medication will be performed ([Table 14](#)). An additional sensitivity analysis will evaluate the effect of recoveries that were not sustained as indicated in Section [3.3.2](#) ([Table 15](#)).

A restricted mean survival time analysis will be performed as an exploratory analysis. The restricted mean recovery time estimates will be provided for each treatment group and baseline disease severity stratum as well as the difference in restricted mean recovery time between treatment groups within each of the severity strata ([Table 16](#)).

In addition, a forest plot will be generated for the “leave one out” sensitivity analyses described in Section [6.7](#) ([Figure 10](#)); hazard ratio estimates and CIs will be provided for each subgroup that leaves a single site out.

Two corroborative summaries will also be generated. A summary of the number and percentage of subjects in each treatment group who recovered (and are alive), did not recover (and are alive), and died by Day 29 will be summarized. The summary will also include the numbers and percentages, grouping deaths and non-recoveries together ([Table 17](#)). The summaries will also be provided by the Modified Oxygen Use ordinal scale and the duration of symptoms categorizations specified in Section [6.4](#).

Other censoring techniques and additional analyses of the primary outcome may be performed.

8.2. Secondary Efficacy Analyses

This section describes the planned analyses for the secondary efficacy outcome measures. Where applicable, refer to Section [6.1](#) for SAS pseudocode. Analyses of mortality will be described in Section [9.4](#).

As noted in Section [3.1](#), the main analysis of the key secondary efficacy outcomes will exclude subjects enrolled with a baseline ordinal score of 6. The main analyses of the remaining secondary efficacy outcomes will be performed in subgroups based on the baseline ordinal score. Analyses will be performed for the 4 or 5 (combined) subgroup separately from the 6 subgroup.

Analyses of the key secondary outcome measure will be explored in the specified subgroups described in Section [6.4](#). Analyses of the other secondary outcome measures will be performed by treatment arm only and repeated for specified subgroups described in Section [6.4](#) and Section [6.7](#) via stratified analyses. As with the analyses described in Section [8.1.2](#), tabular summaries will follow the structure of the main tabular summaries planned for each outcome with the modification that stratified estimates will be provided in separate rows. Forest plots will display confidence intervals of outcomes/estimates across subgroups, where applicable.

All secondary efficacy analyses will be performed in the mITT population. As Treated analyses may be explored to investigate consistency of results compared to the mITT analyses.

8.2.1. Ordinal Scale Outcomes (Key Secondary Outcome Measure)

For the analysis of the first key secondary outcome measure, the distribution of the 8-point ordinal clinical status scale with 8 categories at Study Visit Day 15 (not necessarily actual study day 15), the outcome will be analyzed using a proportional odds model with treatment arm and disease severity as covariates. The treatment odds ratio estimated from the model will be presented along with the p-value ([Table 18](#) and [Table 19](#)). The analysis will be repeated using the modified oxygen use scale. The Study Visit Day 15 clinical status score will be depicted graphically using shifted bar plots; the outcomes will be presented by baseline ordinal score and treatment group ([Figure 11](#)). In addition to the subgroup analyses, the main analysis will be repeated including a treatment * baseline ordinal score interaction term, where the interaction term p-value will be reported for the interaction model.

Multiple supplemental analysis of this key secondary outcome will be performed. Time to improvement by at least one category in the clinical status 8-point scale (see Section [3.3](#)). The log rank test will be performed using a Cox proportional hazards model to test whether the curves differ between treatment arms. The median time to event and CI in each treatment group will be summarized along with the treatment hazard ratio estimate and log rank p-value ([Table 20](#)). Differences in time-to-event endpoints by treatment arm will be summarized with

Kaplan-Meier curves ([Figure 12](#)). Number at risk, hazard ratio and log rank p-values will be presented on the figures. The analyses (and tabular and graphical summaries) will be repeated using the outcome of time to improvement in two categories of the ordinal scale defined in [Section 3.3](#).

The above analyses will be repeated with the Modified Recovery ordinal scale described in [Section 4.3](#) ([Table 21](#)). The only subgroup analysis that will be performed for time to improvement will be an analysis that classifies subjects by the duration of symptoms at baseline subgroups (above/below the median) ([Table 22](#)).

The number and proportion of subjects along with 95% confidence intervals by category of clinical status will be presented by treatment arm at Study Visit (not necessarily actual) Days 1, 3, 5, 8, 11, 15 and 29 ([Table 23](#)). These summaries will be replicated using the Modified Oxygen Use ordinal scale described in [Section 4.3](#). Change from baseline (using the as-reported ordinal scores) will also be summarized at Days 3, 5, 8, 11, 15, 22, and 29 ([Table 27](#)).

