To perform a stratified Cox proportional hazards model for the final analysis and generate the treatment arm hazard ratio along with its confidence interval, the following pseudocode will be used. For any unstratified analyses, code can be used after the removal of the `strata ... ;` line and strata variable in the `class` statement.

```
proc phreg data=dataset;
  class StrataVariable(ref=StrataLabel)
TreatmentVariable(ref=RemdesivirLabel);
  model TimeVariable * CensorVariable(1) = TreatmentVariable;
  strata StrataVariable;
  hazardratio TreatmentVariable / diff=ref cl=Wald;
  ods output HazardRatios = HRest;
run;
```

The following SAS pseudocode will be used to perform the final proportional odds model with treatment arm and disease severity as covariates and to generate the treatment odds ratio, p-value, and predicted probabilities of the ordinal scale levels by treatment arm and disease severity:

```
proc logistic data=dataset
  plots(only)=effect(x=ResponseVariable
    sliceby=DiseaseSeverityVariable*TreatmentVariable individual connect);
  class DiseaseSeverityVariable(param=ref ref=ModerateLabel)
    TreatmentVariable(param=ref ref=RemdesivirLabel);
  model ResponseVariable = TreatmentVariable StrataVariable;
  oddsratio TreatmentVariable;
  ods output OddsRatiosWald = ORest;
run;
```

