The effect of on-study treatment on select efficacy outcomes will also be explored among subjects who reported use of statins, angiotensin receptor blockers (ARBs), or angiotensin converting enzyme inhibitors (ACEIs) via subgroup analyses. These additional concomitant medication analyses will also exclude subjects with a baseline ordinal score of 6.

Lastly, the effect of treatment on the primary and key secondary efficacy outcomes will be explored via regression modeling controlling for age, duration of symptoms prior to randomization, baseline d-dimer, and baseline CRP values as continuous covariates. As with the above, this will exclude subjects with a baseline ordinal score of 6.

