Any Medication of Interest ^d	Interferon beta-1a + RDV (N=X)	x.xx	x.xx, x.xx	--
	Placebo + RDV (N=X)			
Hydroxychloroquine/Chloroquine	Interferon beta-1a + RDV (N=X)	x.xx	x.xx, x.xx	--
	Placebo + RDV (N=X)			
Corticosteroids	Interferon beta-1a + RDV (N=X)	x.xx	x.xx, x.xx	--
	Placebo + RDV (N=X)			
Anti-Inflammatory Drugs	Interferon beta-1a + RDV (N=X)	x.xx	x.xx, x.xx	--
	Placebo + RDV (N=X)			
Covariate-Adjusted Model^c				
Covariate-Adjusted	Interferon beta-1a + RDV (N=X)	x.xx	x.xx, x.xx	--
	Placebo + RDV (N=X)			
Interaction Models				
Treatment-Baseline Ordinal Score Interaction (4 or 5 vs. 6)	Interferon beta-1a + RDV (N=X)	x.xx	x.xx, x.xx	--
	Placebo + RDV (N=X)			
Treatment-Continuous Baseline Ordinal Score (4 or 5) Interaction	Interferon beta-1a + RDV (N=X)	x.xx	x.xx, x.xx	--
	Placebo + RDV (N=X)	x.xx	x.xx, x.xx	
Treatment-Categorical Baseline Ordinal Score (4 or 5) Interaction	Interferon beta-1a + RDV (N=X)	x.xx	x.xx, x.xx	--
	Placebo + RDV (N=X)	x.xx	x.xx, x.xx	

^aAnalysis of key secondary endpoint using those subjects in the mITT Population with baseline ordinal score (actual score) of 4 or 5 with disease severity as a model covariate.

^bThis analysis used a modified version of the ordinal scale where the definitions of categories 5 and 6 are, respectively, “Hospitalized, requiring supplemental oxygen or high flow oxygen devices at oxygen flow rate less than or equal to 15L/min” and “Hospitalized, on non-invasive ventilation or high flow oxygen devices at oxygen flow rate greater than 15L/min”.

^cRestricted to subjects with baseline ordinal score of 4 or 5.

^dExcluding statins, ARBs, and AECIs.

Odds ratios for interaction models are calculated at the level of each individual OS category.

Programming Notes:

For the Main Analysis, the p-value will only be reported if the p-value from the primary analysis of time to recovery (including all three OS strata) is significant. If the p-value will not be reported, then the columns will be removed.

Apart from the “Treatment-Baseline Ordinal Score Interaction (4 or 5 vs. 6)” model, all analyses will be restricted to subjects with a baseline ordinal score of 4 or 5.

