P-value of treatment comparison will only be displayed for the main analysis. For the interaction models, the p-value for the interaction term will be provided in a footnote reading “The p-value for the treatment by baseline ordinal score interaction term was 0.xxx.” or “The p-value for the treatment by [continuous/categorical] baseline ordinal score interaction term was 0.xxx.”.

For the covariate-adjusted model, the model will be run with age, duration of symptoms prior to randomization, baseline d-dimer, and baseline CRP values included as continuous covariates. High sensitivity CRP values are excluded from this analysis (denote this in a footnote).

Table with similar format:

Table 19: Odds Ratio for Better (Lower) Clinical Status Score at Study Visit Day 15 by Treatment Using a Proportional Odds Model, Interferon beta-1a + RDV Relative to Placebo + RDV – As Treated Population

Programming Note: P-value of treatment comparison will only be displayed for the main analysis. For the interaction models, the p-value for the interaction term will be provided in a footnote reading “The p-value for the treatment by baseline ordinal score interaction term was 0.xxx.” or “The p-value for the treatment by [continuous/categorical] baseline ordinal score interaction term was 0.xxx.”.

Table 20: Time to Improvement on the 8-Point Ordinal Scale by Treatment Group

Analysis Population	Baseline Ordinal Score	Treatment Group		Median Time		HR	
			n	Estimate	95% CI	Estimate	95% CI
Improvement by at least One Category							
mITT Population	4 or 5	Interferon beta-1a + RDV (N=X)	x	x.x	x.x, x.x	x.xx	x.xx, x.xx
		Placebo + RDV (N=X)	x	x.x	x.x, x.x		
As Treated Population	4 or 5	Interferon beta-1a + RDV (N=X)	x	x.x	x.x, x.x	x.xx	x.xx, x.xx
		Placebo + RDV (N=X)	x	x.x	x.x, x.x		
mITT Population	6	Interferon beta-1a + RDV (N=X)	x	x.x	x.x, x.x	x.xx	x.xx, x.xx
		Placebo + RDV (N=X)	x	x.x	x.x, x.x		
As Treated Population	6	Interferon beta-1a + RDV (N=X)	x	x.x	x.x, x.x	x.xx	x.xx, x.xx
		Placebo + RDV (N=X)	x	x.x	x.x, x.x		
Improvement by at least Two Categories							
mITT Population	4 or 5	Interferon beta-1a + RDV (N=X)	x	x.x	x.x, x.x	x.xx	x.xx, x.xx
		Placebo + RDV (N=X)	x	x.x	x.x, x.x		
As Treated Population	4 or 5	Interferon beta-1a + RDV (N=X)	x	x.x	x.x, x.x	x.xx	x.xx, x.xx
		Placebo + RDV (N=X)	x	x.x	x.x, x.x		
mITT Population	6	Interferon beta-1a + RDV (N=X)	x	x.x	x.x, x.x	x.xx	x.xx, x.xx
		Placebo + RDV (N=X)	x	x.x	x.x, x.x		

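### The main Day 15 proportional odds model adjusts only for baseline score; age and symptom duration, both collected at screening, are left to an exploratory model, which forgoes some efficiency

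*SAP*

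**What the plan says.** SAP 8.2.1 specifies for Day 15 clinical status that "the outcome will be analyzed using a proportional odds model with treatment arm and disease severity as covariates". Two other places confirm that the model has two terms. The SAP 6.1 code reads "model ResponseVariable = TreatmentVariable StrataVariable", and note a to Table 18 limits the analysis to subjects with "baseline ordinal score (actual score) of 4 or 5 with disease severity as a model covariate". The main analysis leaves out subjects whose baseline score was 6 (SAP 8.2).

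Age and symptom duration enter a Day 15 model as covariates in one place only. SAP 6.4 says that the treatment effect "will be explored via regression modeling", "controlling for age, duration of symptoms prior to randomization, baseline d-dimer, and baseline CRP values as continuous covariates". The Table 18 programming notes repeat this, and they remove high-sensitivity CRP values from that model. They also say: "P-value of treatment comparison will only be displayed for the main analysis". Elsewhere in the Day 15 analysis, age and symptom duration are subgroup factors. No Day 15 model adjusts for them without the laboratory values.

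Both variables are available at baseline. Protocol Appendix C collects demographics at screening (1.2) and the day of symptom onset in the screening history (8.1.1).

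**The concern.** In a proportional odds model, leaving out a baseline covariate that predicts the outcome pulls the treatment odds ratio towards 1 and lowers the power of its test. Adding one that predicts nothing costs almost nothing. The documents give some reason to expect that age predicts: protocol Appendix C 5.2.1 remarks that severe COVID-19 falls mainly on older adults. The SAP gives no reason for keeping age and symptom duration out of the one Day 15 model that carries a p-value.

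The exploratory model is a weak substitute because it ties the two screening covariates to two laboratory values. One site ran both standard and high-sensitivity CRP, and the high-sensitivity results are excluded from any analysis that uses CRP (SAP 4.3). Subjects without a usable value could drop out of the adjusted model. The documents do not say how many.

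**Working it through.** **Inputs from the documents.** Two-sided alpha 0.05; 1:1 allocation; control distribution Scenario 1, worst to best 2, 1, 2, 7, 8, 10, 30, 40%; stated N of 396 for 85% power at an odds ratio (OR) of 1.75; planned total about 923 (protocol Appendix C 9.2).

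**Reproducing the stated figure.** The protocol's formula is N = 12(z_α/2 + z_β)² / {λ²(1 − Σp_i³)}, where λ is the log OR and p_i is averaged over arms. It has no covariate term. For OR 1.75:
- 12 × (1.960 + 1.036)² = 107.7
- λ² = 0.3132
- Σp_i³ = 0.127
- N = 107.7 / (0.3132 × 0.873) = 394, against 396 stated

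The other cells of the sample size table also reproduce to within about 3 subjects. Power at 396 is 85.2%.

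**Main-model power at the planned size.** If N₈₅ is the formula's N for 85% power, power at N is Φ{2.996 × √(N/N₈₅) − 1.960}.
- OR 1.75: 2.996 × √(923/394.1) − 1.960 = 2.63, so 99.6%
- OR 1.5: 2.996 × √(923/741.8) − 1.960 = 1.38, so 91.7%

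The same calculation gives 70.0% at OR 1.35 and 45.7% at 1.25. The smallest OR with 85% power at 923 is about 1.44. If 10% of the 923 had baseline score 6, the Day 15 analysis would hold about 831, and power would be 99.2% (OR 1.75), 88.7% (1.5), 65.4% (1.35) and 41.9% (1.25).

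**Gain from the two covariates.** This was simulated with 923 patients, Scenario 1 and 1,500 trials per setting. Treatment plus baseline score was compared with the same model plus age and symptom duration as continuous terms. The treatment effect was set so that the main-model OR matched the target. Assumptions not in the documents: 80% of subjects at score 5, OR 2.5 for score 5 against 4, and the covariate strengths below. The effective-sample ratio is the squared ratio of mean z-statistics.

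| Age / duration, log-OR per SD | Effective-sample gain |
|---|---|
| 0 / 0 | none (ratio 0.999) |
| 0.2 / 0.1 | about 1.6% |
| 0.4 / 0.2 | about 6% |
| 0.6 / 0.3 | about 14% |
| 0.8 / 0.3 | about 23% |

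**Power (%) at 923, with N multiplied by (1 + gain) in the formula.** For example, at OR 1.5 and a 23% gain: 3.342 × √1.23 − 1.960 = 1.75, so 96.0%.

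| OR | Main model | 1.6% | 6% | 14% | 23% |
|---|---|---|---|---|---|
| 1.25 | 45.7 | 46.3 | 47.8 | 50.7 | 53.7 |
| 1.35 | 70.0 | 70.6 | 72.5 | 75.5 | 78.6 |
| 1.5 | 91.7 | 92.1 | 93.1 | 94.6 | 96.0 |
| 1.75 | 99.6 | 99.6 | 99.7 | 99.8 | 99.9 |

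**Cost of missing laboratory values.** Suppose 10% of subjects dropped out of the adjusted model (assumed). Simulated power at OR 1.35 for the main model, the adjusted model on everyone, and the adjusted model on 90% was:
- 0.4/0.2: 68.6, 71.7 and 67.8%
- 0.6/0.3: 66.8, 73.7 and 70.0%

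At weak and middle strengths the loss cancels or reverses the gain; at stronger ones it reduces it. This run counts only the lost subjects and credits d-dimer and CRP with no prognostic value of their own.

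**The case against.** The strongest reply is that the SAP follows the protocol. Appendix C 9.4.3 describes a proportional odds model by disease strata with a stratified test, and the ACTT-2 appendix describes the same. This stands in part: the change needs matching protocol wording, and the ACTT-3 main model would then differ from the one described for ACTT-2.

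A second reply is that power is already ample. At the planning OR of 1.75 this is correct, because the recovery target drives enrolment to about 923 against the 396 needed. A reader might infer that the Day 15 analysis is underpowered or that 396 is wrong. The documents support neither: the figure reproduces, and at OR 1.75 the gain is at most 0.3 points. Smaller effects are still plausible. ACTT-1 observed an OR of 1.50 with a recovery rate ratio of 1.29 (SAP 2), and ACTT-3 assumes a rate ratio of only 1.25 because a second agent is unlikely to match the first.

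A third reply is that the strength of the covariates is assumed. This stands. A reader might infer that the SAP itself regards age and symptom duration as prognostic. It does not say so: it uses them as subgroup factors, which address effect modification, and in an exploratory model. The protocol's remark on older adults is qualitative, and no effect size is given for either variable. Baseline score, already in the model, may also capture part of the prognosis.

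Fourth, a covariate-adjusted OR with a confidence interval is already planned in Table 18, the high-sensitivity CRP problem is described for one site, and SAP 6.5 has a rule for missing baseline d-dimer and CRP (written for the laboratory outcomes). These points limit the laboratory complaint. They do not supply an age-and-duration model free of laboratory values.

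Finally, the Day 15 p-value is reported only if the primary test is significant (SAP 6.8), so the powers above are not those of the whole planned procedure.

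**Conclusion.** The point holds as a missed efficiency gain. Its size cannot be derived from the documents. Over the assumed range the effective-sample gain is about 0 to 23%. For moderate to strong covariate effects (gains of 6 to 23%), power rises by about 1 to 4 points at OR 1.5 and 2 to 9 points at OR 1.25 to 1.35. For weak effects, and at OR 1.75, the gain is close to nil. With no prognostic value the cost is negligible. All of this rests on Scenario 1, the assumed covariate strengths and baseline-score mix, and N near 923 before removing subjects with baseline score 6.

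A reader might extend the argument to the mortality analyses. Nothing calculated here bears on them.

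**What to change.** Before unblinding, define the main model in SAP 8.2.1 as treatment, baseline score, age (continuous) and symptom duration (continuous), and attach the gated p-value to it. Change the model line in SAP 6.1 and note a of Table 18 to match, and align the wording of protocol Appendix C 9.4.3. Keep the severity-only model and the d-dimer/CRP model as sensitivity rows in Table 18.

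The cost is wording and one line of code; no new data are needed. The downsides should be stated. The odds ratio becomes conditional on two more covariates and will tend to lie further from 1 (at the strongest assumed setting, about 1.59 where the main model gives 1.5). A linear form is assumed for both covariates. The model will also differ from the severity-only one described for ACTT-2, and keeping that model as a sensitivity row preserves the comparison. Because the two odds ratios can differ, the choice of main model must be fixed in advance.

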8.2.2. NEWS

The median time to discharge or to a NEWS of ≤ 2 and CI will be summarized by treatment group ([Table 29](#)). The hazard ratio and log rank p-values will be provided with the summaries. Differences in time-to-event endpoints by treatment arm will be summarized with Kaplan-Meier curves. Number at risk, hazard ratio and log rank p-values will be included on the figures ([Figure 16](#)).

The mean, confidence interval, median, minimum, and maximum NEWS at Baseline and Study Visit (not necessarily actual) Days 3, 5, 8, 11, 15 and 29 will be presented by treatment arm as well as change from baseline at each post-Day 1 visit ([Table 31](#)). A figure with mean and confidence interval over time will also be presented by treatment arm ([Figure 18](#)).

Subject listings of NEWS responses (overall and individual components) by day will be generated ([Listing 6](#)).

